6.2.3. Vital Signs

The subject incidence rate of >5% weight loss or gain on study will be provided, as well as whether weight loss was explained or unexplained.

6.2.4. Local Tolerance Assessments

For both the Investigator and Subject assessment of the numeric application site reaction, scores will be summarized individually by using number and percentage of subjects by visit, as well as mean/median scores.

6.2.5. Medical History and Physical Examinations

Medical history for all subjects will be presented in a by-subject listing.

Clinically significant changes observed during physical examination will be captured as adverse events and included in AE tabulations.

6.3. Efficacy Evaluation

Efficacy analyses will be conducted in the Intent-to-Treat (ITT) population.

6.3.1. Co-Primary Endpoints

The co-primary efficacy endpoints in this study are

1. S-IGA Success, defined as achievement of Scalp-IGA (S-IGA) score of 'Clear' or 'Almost Clear' plus a 2-grade improvement from Baseline.
2. B-IGA Success, defined as Achievement of Body-IGA (B-IGA) score of 'Clear' or 'Almost Clear' plus a 2-grade improvement from Baseline.

The primary estimands are the odds of achieving S-IGA success at 8 weeks and the odds of achieving B-IGA success at 8 weeks; that is, the ratio of the odds of achieving S-IGA success at 8 weeks roflumilast foam 0.3% relative to the odds of success at 8 weeks of using a matching vehicle cream (similarly for B-IGA). In the course of the 8-week randomized treatment period, subjects may be exposed to possible known or unknown intercurrent events that could possibly impact the estimand, such as treatment discontinuation due to a specific adverse effect or perhaps a lack of effect. The "Treatment Policy Strategy" has been adopted for handling all known or unknown intercurrent events in this study. To this end, the ITT principle will serve as the analytical basis for interpreting the estimand. In other words, the odds ratio of achieving S-IGA Success and the odds ratio of achieving B-IGA Success for roflumilast foam 0.3% relative to vehicle at 8 weeks will be evaluated regardless of the occurrence of any such intercurrent event. This estimand shall be estimated using the CMH approach. This approach produces an estimate that is the combined odds ratio resulting from adjusting for the possible effects of 3 classification factors: pooled site group, baseline S-IGA category (3 vs. 4) and baseline B-IGA category (2 vs. ≥ 3). S-IGA and B-IGA will be tested separately, but both endpoints must be statistically significant at the 2.5% level for the study to be considered a success.

6.3.2. Secondary Endpoint

Continuous secondary and exploratory endpoints will be analyzed using Analysis of Covariance with treatment and the stratification factors as independent variables. The ITT population will be used, and missing data will be imputed using multiple imputation. Binary secondary and exploratory endpoints will be analyzed similarly to the primary endpoint. To control for multiple comparisons among the secondary endpoints, the following testing plan will be used:

Upon demonstration of statistical significance for S-IGA Success at Week 8 at the 2.5% level and statistical significance of B-IGA Success at Week 8 at the 2.5% level, the testing scheme described below will be used to test the secondary endpoints. This testing scheme will control the overall type 1 error at the 0.025 level.

The overall α level of 0.025 will be split to test 3 families of secondary endpoints, and the Fallback Method will be applied.

Family 1 ($\alpha=0.01$ or $\alpha = 0.015$):

- For subjects with Baseline Scalp Itch (SI) NRS score ≥ 4 , achievement of ≥ 4 -point improvement from Baseline in SI-NRS at Week 8 (“SI-NRS Success at Week 8”)
- SI-NRS Success at Week 4
- SI-NRS Success at Week 2
- SI-NRS Change from Baseline (CFB) at Week 1
- SI-NRS CFB at 72 hours

Family 2 ($\alpha=0.005$):

- For subjects with Baseline WI-NRS score ≥ 4 , achievement of ≥ 4 -point improvement from Baseline in WI-NRS at Week 8 (“WI-NRS Success at Week 8”)
- PASI-75 at Week 8
- CFB in PSD Items related to Itching, Pain, and Scaling (Questions 1, 9, and 11) aggregate score at Week 8
- PSD Item related to Scaling (Question 11) = 0 at Week 8
- PSD Item related to Itching (Question 1) = 0 at Week 8
- PSD Item related to Pain (Question 9) = 0 at Week 8
- PSSI-75 at Week 8

Family 3 ($\alpha=0.01$ or 0.015 or 0.025):

- S-IGA score of ‘clear’ at Week 8
- S-IGA Success at Week 4
- CFB in PASI at Week 2
- S-IGA Success at Week 2
- PSD Total Score = 0 at Week 8
- SI-NRS CFB at Day 1

The Fallback Method will be used to pass unused alpha across the Families. The Families will be tested in this order: Family 2, Family 1, Family 3. Testing will be sequential within Family 2 and Family 1, with the order of testing of each endpoint within each family as listed above.

Testing within Family 3 will be implemented with Holm’s procedure.

To start, Family 2 will be tested, sequentially within Family 2, each endpoint at the $\alpha=0.005$ level. Should the testing succeed through all seven endpoints in Family 2, the $\alpha=0.005$ will remain unused, and will be passed to Family 1.

The testing of the five SI-NRS endpoints in Family 1 will be sequential, either at the $\alpha=0.01$ level (assumes Family 2 had an unsuccessful test), or the $\alpha=0.015$ level (assumes all endpoints in Family 2 were successful at the $\alpha=0.005$ level).

Family 3 contains six endpoints. Family 3 has initially been allocated $\alpha=0.01$. This creates three possible testing alpha levels for the Family 3 endpoints:

- If all tests in Family 1 ($\alpha=0.01$) and Family 2 ($\alpha=0.005$) are successful, then $\alpha=0.005+0.01=0.015$ is unused, and the $\alpha=0.015$ will be carried to Family 3, allowing Family 3 endpoints to be tested at the full 0.025 level.
- If the $\alpha=0.005$ in Family 2 is used, but the subsequent $\alpha=0.01$ allocated to Family 1 is not used, then Family 3 endpoints will be tested at the $\alpha=0.01+0.01=0.02$ level.
- If the $\alpha=0.01$ in Family 1 is used, and the $\alpha=0.005$ in Family 2 is also used, then Family 3 endpoints will be tested at $\alpha=0.01$.

Descriptive statistics will be presented for endpoint and safety data collected in the clinical study. This includes the number and percentage of subjects for binary endpoints/categorical data, and mean, SD, median, Q1, Q3, minimum, and maximum for continuous data.

All subjects who are randomized and receive at least one confirmed dose of investigational product will be included in the safety population.

Adverse events (AEs) will be summarized by preferred term, system organ class, and treatment group for all treatment-emergent AEs, serious AEs, related AEs, AEs leading to withdrawal from investigational product.

Safety laboratory parameters and vital signs will be summarized at each visit using descriptive statistics or frequencies and percentages, as appropriate. Changes from Baseline and percent changes from Baseline in laboratory values and vital signs will also be summarized by visit. In addition, changes from Baseline and percent changes from Baseline in weight and laboratory values will be summarized using shift tables.

Descriptive statistics will be calculated for the PHQ-8 (adults) and Modified PHQ-A (adolescents). The C-SSRS will be analyzed per the Scoring and Data Analysis Guide from the Columbia Lighthouse Project.

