4. STATISTICAL ANALYSIS AND REPORTING

4.1. Introduction

Data processing, tabulation of descriptive statistics, calculation of inferential statistics, and graphical representations, will be performed primarily using SAS (release 9.4 or higher). If the use of other software is warranted for analyses conducted by Premier Research, the final statistical methodology report will detail what software was used for what purposes.

Continuous (quantitative) variable summaries will include the number of subjects (n) with nonmissing values, mean, standard deviation (SD), median, minimum, maximum, first quartile (Q1), and third quartile (Q3).

Categorical (qualitative) variable summaries will include the frequency and percentage of subjects who are in the particular category or each possible value. In general, the denominator for the percentage calculation will be based upon the total number of subjects in the study population for the treatment group, unless otherwise specified.

Unless otherwise indicated, all statistical tests will be conducted at the familywise $\alpha=0.025$ significance level using 2-tailed tests, and P values will be reported. Corresponding 95% and 97.5% confidence intervals will be presented for statistical tests. Details for splitting the familywise α to control for multiple comparisons will be discussed in [Section 6.1.3](#).

All data collected in the electronic case report form (eCRF) will be provided in subject listings.

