6.1.3. Multiple Comparisons

Upon demonstration of concurrent statistical significance for S-IGA Success at Week 8 at the 2.5% level, and statistical significance of B-IGA Success at Week 8 at the 2.5% level, the testing scheme described below will be used to test these secondary endpoints. This testing scheme will control the overall type 1 error at the 0.025 level.

The overall α level of 0.025 will be split to test 3 families of secondary endpoints, and the Fallback Method will be applied across the families.

Family 1 ($\alpha=0.01$ or 0.015):

- SI-NRS Success at Week 8
- SI-NRS Success at Week 4
- SI-NRS Success at Week 2
- SI-NRS change from baseline (CFB) at Week 1
- SI-NRS CFB at 72 hours

Family 2 ($\alpha=0.005$):

- WI-NRS Success at Week 8
- PASI-75 at Week 8
- CFB in PSD Items related to Itching, Pain, and Scaling (Questions 1, 9, and 11) aggregate score at Week 8
- PSD Item related to Scaling (Question 11) = 0 at Week 8
- PSD Item related to Itching (Question 1) = 0 at Week 8
- PSD Item related to Pain (Question 9) = 0 at Week 8
- PSSI-75 at Week 8

Family 3 ($\alpha=0.01$ or 0.02 or 0.025):

- S-IGA score of “Clear” at Week 8
- S-IGA Success at Week 4

- CFB in PASI at Week 2
- S-IGA Success at Week 2
- PSD Total Score = 0 at Week 8
- SI-NRS CFB at Day 1

The Fallback Method will be used to pass unused alpha across the Families. The Families will be tested in this order: Family 2, Family 1, Family 3. Testing will be sequential within Family 2 and Family 1, with the order of testing of each endpoint within each family as listed above.

Testing within Family 3 will be implemented with Holm's procedure.

To start, Family 2 will be tested, sequentially within Family 2, each endpoint at the $\alpha=0.005$ level. Should the testing succeed through all seven endpoints in Family 2, the $\alpha=0.005$ will remain unused, and will be passed to Family 1.

The testing of the five SI-NRS endpoints in Family 1 will be sequential, either at the $\alpha=0.01$ level (assumes Family 2 had an unsuccessful test), or the $\alpha=0.015$ level (assumes all endpoints in Family 2 were successful at the $\alpha=0.005$ level).

Family 3 contains six endpoints. Family 3 has initially been allocated $\alpha=0.01$. This creates three possible testing alpha levels for the Family 3 endpoints:

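### Protocol 6.3.2 lists a Family 3 testing level of 0.015 that the fallback never produces; the bullets below it and the SAP give 0.02

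*Protocol*

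**What the plan says.** Protocol 6.3.2 splits 0.025 over three families of secondary endpoints. The headings begin "Family 2 ($\alpha=0.005", "Family 1 ($\alpha=0.01$ or $\alpha = 0.015" and "Family 3 ($\alpha=0.01$ or 0.015 or 0.025". Families are tested in the order 2, 1, 3. Families 2 and 1 are tested sequentially, and the six endpoints of Family 3 by Holm's procedure. If all seven Family 2 endpoints succeed, their 0.005 "will remain unused, and will be passed to Family 1".

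Three bullets then set the Family 3 level: 0.025 if Families 1 and 2 both succeed, 0.02 if Family 2 fails and Family 1 succeeds, and 0.01 if both fail. The last bullet opens "If the $\alpha=0.01$ in Family 1 is used, and the $\alpha=0.005$ in Family 2 is also used". In this text, alpha counts as used when a family has a failed test and as unused when every test in it succeeds.

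SAP 6.1.3 repeats the bullets, but its heading reads "Family 3 ($\alpha=0.01$ or 0.02 or 0.025". Every Family 3 row of SAP Table 5 carries the same three levels. The protocol synopsis heading shows only the initial 0.01 and has the same bullets. The SAP states: "This testing scheme will control the overall type 1 error at the 0.025 level".

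**The concern.** The heading gives a decision threshold for six secondary endpoints, and it disagrees with the bullets in its own section and with the SAP. It is not a text-extraction error, because the Amendment 3 summary of changes records the same addition. SAP section 11, which lists changes from the planned analysis, does not mention the difference.

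The stray figure matters more because one outcome has no bullet of its own. Families 2 and 1 can each succeed or fail, giving four outcomes, and the bullets describe three. The missing one is full success in Family 2 followed by failure in Family 1. The third bullet does not literally fit, since it requires Family 2's alpha to have been used. The stray level equals 0.01 + 0.005, which is what someone would get by handing Family 2's alpha to Family 3 after it had already gone to Family 1. At stake are the Holm thresholds for Family 3 and the stated control at 0.025.

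**Working it through.** **Inputs.** Initial levels are 0.005 (Family 2), 0.01 (Family 1) and 0.01 (Family 3), with testing order 2, 1, 3, from protocol 6.3.2 and SAP 6.1.3. Tests are two-sided: SAP 4.1 says "all statistical tests will be conducted at the familywise $\alpha=0.025$ significance level using 2-tailed tests".

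**Step 1: the plan's own total.** 0.005 + 0.01 + 0.01 = 0.025. This reproduces.

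**Step 2: the fallback over all four outcomes.** Family 1 level = 0.01, plus 0.005 if Family 2 fully succeeds. Family 3 level = 0.01, plus the whole Family 1 level if Family 1 fully succeeds.

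| Family 2 | Family 1 | Family 1 level | Family 3 level | Bullet in the documents |
|---|---|---|---|---|
| succeeds | succeeds | 0.015 | 0.01 + 0.015 = 0.025 | yes, 0.025 |
| fails | succeeds | 0.01 | 0.01 + 0.01 = 0.02 | yes, 0.02 |
| fails | fails | 0.01 | 0.01 | yes, 0.01 |
| succeeds | fails | 0.015 | 0.01 | none |

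The three bulleted levels reproduce exactly. No row gives 0.015.

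**Step 3: consequence if 0.015 were misapplied to the last row.** Suppose the Family 2 effects are real and always detected, the Family 1 endpoint reached at 0.015 is null, and Family 3 endpoints are null.

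- Bonferroni bound: 0.015 + 0.015 = 0.030, against 0.015 + 0.01 = 0.025 with Family 3 at 0.01.
- Independent tests, six Family 3 nulls under Holm: 1 − (1 − 0.015)(1 − 0.015/6)^6 = 0.0297, against 1 − (1 − 0.015)(1 − 0.01/6)^6 = 0.0248.
- One Family 1 null and one Family 3 null, correlated two-sided tests (bivariate normal), Family 3 at 0.015: 0.0298 at correlation 0, 0.0283 at 0.5, and below 0.025 once the correlation exceeds about 0.78.

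**Step 4: consequence if 0.015 replaced 0.02 in the second row.** Holm's first threshold would be 0.015/6 = 0.0025 instead of 0.02/6 = 0.0033. That is conservative: it gives up alpha and does not inflate error.

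**The case against.** The strongest reply is that this is one wrong number in one heading. Protocol 6.1 describes its methods as a summary of the fuller SAP, and the SAP has the right levels in both places where it lists them. The bullets, which are the operative rules, agree in the synopsis, protocol 6.3.2 and SAP 6.1.3, and the second bullet writes out its sum to 0.02. All of that stands, and it makes misuse unlikely. It does not make the heading correct.

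A reader might infer that the Family 3 level is undefined after Family 2 succeeds and Family 1 fails. The documents do not support that. Family 3 starts at 0.01, Family 2's alpha is passed only to Family 1, and the Fallback Method is named, so a failure in Family 1 leaves nothing to carry forward. The reference to three possible levels is also right, because the four outcomes map to three levels. What is missing is one explicit route to 0.01.

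How likely that outcome is cannot be judged from the documents. They give no effect size for the 72-hour change in scalp itch that closes Family 1, and claim at least 90% power only for most secondary endpoints. Where the 0.015 came from is also unknown: it could be a slip from Family 1's level or from the 0.015 carried forward in the first bullet.

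**Conclusion.** The concern holds as an error in the protocol 6.3.2 heading: 0.015 should be 0.02. The unlisted fourth outcome is a point of clarity, because the pre-specified method already gives 0.01.

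A reader might go further and conclude that the plan fails to control error at 0.025. It does not fail as written. No sentence assigns 0.015 to the fourth outcome. The 0.030 figure requires an analyst to prefer the protocol heading to the SAP and to the protocol's own bullets, and to count Family 2's 0.005 twice. It is also a worst case, resting on true nulls in Families 1 and 3, detected effects throughout Family 2, and tests that are at most moderately correlated. Co-primary testing is not affected.

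**What to change.** In the protocol 6.3.2 heading for Family 3, change 0.015 to 0.02, so that it matches the bullets below it and the SAP.

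In the synopsis, protocol 6.3.2 and SAP 6.1.3, add one sentence: if all of Family 2 succeeds and Family 1, tested at 0.015, does not, Family 3 is tested at its initial 0.01.

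The cost is wording only, with no new analysis. Timing calls for some care. SAP section 1 records unblinding on 12-Sep-2022, and version 3.0 came after it, so any addition to the testing rules needs a reason on file. The note should say that 0.01 follows from the Fallback Method already specified and is not a new rule. As 0.01 is the lowest Family 3 level in the scheme, stating it cannot favour the product.

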7. STUDY ADMINISTRATION

7.1. Ethics

7.1.1. Ethics Review Board

Before screening of subjects into the study, the current protocol, ICF/assent, and any accompanying material to be provided to the subjects will be reviewed and approved by an appropriate IRB/ERB, as required by FDA (21 CFR § 56) or Health Canada and ICH GCP regulations. A letter documenting the IRB approval must be received by the Sponsor before the

initiation of the study at a study site. Amendments to the protocol will be subject to the same requirements as the original protocol.

The Investigator, Sponsor, or designee will submit a progress report at least once yearly to the IRB. However, the frequency of these reports will depend on IRB requirements. As soon as possible after completion or termination of the study, the Investigator will submit a final report to the IRB per the IRB requirements, and in compliance with FDA and ICH GCP guidelines.

The Investigator, Sponsor, or designee shall promptly notify the IRB of any SAEs, SUSARs, or any other information that may affect the safe use of the study drug(s) during the study, per the IRB local requirements, and in compliance with FDA regulations and ICH GCP guidelines.

7.1.2. Ethical Conduct of the Study

This research will be conducted in accordance with the protocol, the principles of the Tri-Council Policy Statement, the ethical principles set forth in the Declaration of Helsinki, and the ICH harmonized tripartite guideline regarding GCP (E6 (R2), December 2016).

7.1.3. Subject Information and Consent/Accent

The Investigator is responsible for obtaining written informed consent or assent (for adolescents) from everyone participating in this study after adequate explanation (in non-technical terms) of the aims, methods, objectives, and potential hazards of the study and before undertaking any study-related procedures. The Investigator must use the most current IRB or ERB-approved consent/assent forms for documenting written informed consent and assent (for adolescents). Subjects will be assured that they may withdraw from the study at any time without jeopardizing their medical care. Each informed consent (or assent as applicable) will be read, appropriately signed, and dated by the subject or the subject's legally authorized representative and the person conducting the consent discussion, and by an impartial witness if required by the IRB/ERB local requirements.

Subjects will be given a copy of their ICF/assent.

7.2. Study Completion and Termination

7.2.1. Study Completion

The study is considered completed with the last visit of the last subject participating in the study. The final data from the study site will be sent to the Sponsor (or designee) after completion of the final subject visit at that site, in the time frame specified in the Clinical Trial Agreement.

7.2.2. Study Termination

The Sponsor reserves the right to close the study site or terminate the study at any time for any reason at the sole discretion of the Sponsor. Study sites will be closed upon study completion. A study site is considered closed when all required documents and study supplies have been collected and a site closure visit has been performed. The Investigator may initiate site closure at any time, provided there is reasonable cause and sufficient notice is given in advance of the intended termination.

Reasons for the early closure of a study site by the Sponsor or Investigator may include but are not limited to:

- Failure of the Investigator to comply with the protocol, the Sponsor's procedures, or GCP guidelines.
- Inadequate recruitment of subjects by the Investigator.
- Discontinuation of further drug development.

7.3. Study Monitoring

Prior to the initiation of the clinical investigation, Sponsor representatives or designees may visit the study site where the investigation is to be conducted. Sponsor representatives or designees shall ensure that the Investigator understands the investigational status of the investigational product, all requirements of the investigation to be undertaken, and all of his/her responsibilities as an Investigator. Sponsor representatives or designees will also visit the study site at appropriate intervals as required to ensure compliance with the protocol and to verify the accuracy and completeness of data reported on the eCRFs. The Study Director or designees shall be available for consultation with the Investigator and serve as liaisons between the study site and the Sponsor.

The Sponsor or authorized designees may inspect all documents and records required to be maintained by the Investigator, including but not limited to medical records (office, clinic, or hospital) and investigational product dispensation logs for the subjects in this clinical investigation. The Investigator must permit access to such records. The Investigator must obtain, as part of informed consent, permission for an authorized representative of the Sponsor, or regulatory authorities, to review, in confidence, any records identifying subjects.

7.4. Data Quality Assurance

To ensure the collection of adequate, consistent, complete, and reliable data during this clinical investigation, Sponsor representatives or designees may conduct audits of participating sites at appropriate intervals throughout the study. The results of these periodic site audits may be subject to review by independent auditors at completion of the clinical investigation.

All clinical data will undergo a quality control check prior to clinical database lock. Edit checks are performed for appropriate databases as a validation routine to check for missing data, data inconsistencies, data ranges etc. Corrections are made prior to database lock.

7.5. Data Handling and Record Keeping

During the clinical study, the Investigator will maintain adequate source records, including medical records, records detailing the progress of the study for each subject, laboratory reports, signed informed consent/assent forms, IP disposition records, correspondence with the IRB or IEC and Study Monitor/Sponsor, AE reports, and information regarding subject discontinuation and completion of the clinical study.

All required study data will be recorded on eCRFs. Any change of data will be recorded on the audit trail and a reason for the change will be entered.

The Principal Investigator must retain all documentation relating to the study for a period of at least 2 years after the last marketing application approval or, if not approved, 2 years following the discontinuance of the IP. If this requirement differs from any local regulations, the local regulations will take precedence unless the local retention policy is less than 2 years.

